5.5.3. Endpoints Related to Inflammatory Biomarkers

For C-reactive protein (CRP) and fecal calprotectin, the following will be evaluated over all applicable timepoints:

- Change from baseline in CRP concentration [mg/L] over time
- Change from baseline in CRP concentration [mg/L] over time for participants with baseline CRP >3 mg/L
- CRP normalization over time for participants with baseline CRP >3 mg/L, where CRP normalization is defined as CRP ≤ 3 mg/L
- Decrease in CRP concentration of at least 50% relative to baseline among those with a baseline CRP >3 mg/L
- Decrease in CRP concentration of at least 75% relative to baseline among those with a baseline CRP $>3\,$ mg/L

- Change from baseline in fecal calprotectin concentration [mg/kg] over time
- Decrease in fecal calprotectin concentration of at least 50% relative to baseline among those with a baseline fecal calprotectin >250 mg/kg
- Decrease in fecal calprotectin concentration of at least 75% relative to baseline among those with a baseline fecal calprotectin >250 mg/kg
- Change from baseline in fecal calprotectin concentration [mg/kg] over time for participants with baseline fecal calprotectin >250 mg/kg
- Fecal calprotectin ≤150 mg/kg over time for participants with baseline fecal calprotectin >150 mg/kg
- Fecal calprotectin ≤250 mg/kg over time for participants with baseline fecal calprotectin >250 mg/kg

5.5.4. Analysis Methods

Unless otherwise specified, the exploratory endpoints listed and defined in Sections 5.5.1 to 5.5.3 will be analyzed based on the FAS according to the randomized intervention group, regardless of the intervention actually received.

No confirmatory tests will be performed on exploratory endpoints, regardless of the significance for primary and secondary endpoints. Nominal p-values will be presented without adjustments for multiple comparisons.

Descriptive statistics (mean, median, SD, IQ range, minimum, and maximum) will be used to summarize continuous variables. Counts and percentages will be used to summarize categorical variables. Graphical data displays (e.g., line plots) may also be used to summarize the data.

Binary endpoints

The main estimand approach and the estimator used for the secondary endpoints (Section 5.4.1.2) will be used to summarize and compare binary endpoints. Intercurrent events will be handled as specified in Table 6.

The handling of ICEs specified in Section 5.4.1.2 will be applied to each of the above binary endpoints. Participants with ICEs in categories 1-4 and 6 will be considered not to have achieved the binary endpoint, while observed values will be used for participants experiencing an ICE in category 5.

Participants with any missing data for an endpoint after application of ICE handling rules will be imputed as not having achieved the associated binary endpoint. Binary endpoints will be summarized with the number and percentage of participants who achieve the endpoint by intervention group. To compare the proportion of participants achieving the endpoints, MH tests stratified by the ADT-IR status (Yes/No), and Mayo endoscopy subscore at baseline (moderate [2] or severe [3]) will be provided. In case of rare events, Fisher's exact test will be used for intervention comparisons.

Continuous endpoints

For continuous endpoints, handling rules for ICEs as defined in Table 6:

- Composite strategy (categories 1-4 and 6): Baseline values will be assigned from the point of ICE onward
- Treatment policy strategy (category 5): Observed values will be used, if available

To account for missing data (after applying ICE handling strategies) for continuous endpoints that are collected at multiple post-baseline time points through Week 24 / Week 48, an MMRM will be used, under the MAR assumption, to compute nominal p-values between both guselkumab SC groups and placebo SC. The model will include all available data from all intervention groups through Week 24 / Week 48 for assessing efficacy. Missing data will thus not be imputed but rather accounted for through correlation of repeated measures in the model. Additionally, if the MMRM normality assumption is in question, an appropriate transformation may be implemented before fitting the MMRM.

The MMRM will include intervention group, respective baseline score, visit and interaction between visit and intervention group as categorical variables as well as ADT-IR status (Yes/No), and Mayo endoscopy subscore at baseline (moderate [2] or severe [3]). An unstructured covariance matrix for repeated measures within a participant will be used. The F-test will use Kenward-Roger's approximation for the degrees of freedom. In case of lack of convergence, empirical structured covariances will be used in the following order until convergence is reached: 1) Toeplitz; 2) first order autoregressive moving average.

Endpoints that are measured at only one of the visits at Week 12 or Week 24 (e.g., histology based endpoints as described in Section 5.5.1.2) will be compared between the guselkumab SC group(s) and the placebo group using an analysis of covariance (ANCOVA) with treatment group, ADT-IR status (Yes/No), Mayo endoscopy score at baseline (moderate [2] or severe [3]), and corresponding baseline value as covariates.

For analyses using ANCOVA, unless otherwise specified, multiple imputation (same as defined in Section 5.3.3.3.3) will be used for missing data (after applying ICE strategies), under the assumption that the data are missing at random. The analysis will impute the missing score at the respective Week using the corresponding value at baseline and related component score at intermediate visits if applicable, ADT-IR status, Mayo endoscopy score at baseline, and treatment group.

The intervention difference between each guselkumab SC group and placebo SC will be estimated by the difference in the least squares means (LSmeans). The 95% 2-sided CI for the differences in LSmeans and p-values will be calculated based on the MMRM / ANCOVA, as applicable.

Ordinal endpoints

For ordinal endpoints, handling rules for ICEs as defined in Table 6:

- Composite strategy (categories 1-4 and 6): Baseline values will be assigned from the point of ICE onward
- Treatment policy strategy (category 5): Observed values will be used, if available

The intervention comparison between the guselkumab SC groups with placebo SC will be performed using a CMH χ^2 test (row mean scores differ as a hypothesis test for the CMH statistics) stratified by ADT-IR status (Yes/No), and Mayo endoscopy subscore at baseline (moderate [2] or severe [3]). In case of rare events, Fisher's exact test will be used for intervention comparisons. Missing data (after applying the ICE handling strategies) will not be imputed for ordinal endpoints.

Time to event endpoints

The time to event is defined as the time from Week 0 study intervention administration to the date of the first event that occurred through Week 24 / Week 48. Participants who had not had an event by that timepoint or who had terminated study participation prior to having an event will be censored at the last measurement prior to or at that timepoint or their termination date, as applicable.

Participant data will be censored at last measurement prior to or at the time of any ICE in categories 1-4 and 6. Kaplan-Meier (KM) curves will be generated by study intervention group for time to event endpoints. KM-estimates and corresponding p-values will be provided.

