2. A prohibited change in medications for UC (as	treated as an unfavorable outcome
defined in Appendix 14)	
3. Discontinuation from study intervention due to lack	
of efficacy or an adverse event (AE) of UC worsening	
4. Meeting rescue criteria (as determined by the IWRS)	
(Note: Since rescue criteria are assessed at Week 16	
for all participants, this ICE is not applicable for the	
primary endpoint or any of the key secondary Week 12	
endpoints)	
5. Discontinuation of study intervention due to	Treatment policy strategy: Observed values will be
COVID-19 related reasons (excluding COVID-19	used if available
infection) or regional crisis	
6. Discontinuation of study intervention due to reasons	Composite strategy: Occurrence of these ICEs will be
other than ICEs 3 or 5 as described above	treated as an unfavorable outcome

The composite strategy assesses the treatment effect not only based on the variable measurements, but also on ICEs. This estimand acknowledges that having an ICE in categories 1-4 and 6 is an unfavorable outcome. For participants experiencing an ICE in category 5, the treatment policy strategy considers the occurrence of ICE category 5 as irrelevant in defining the treatment effect.

v) Population-level summary: Difference in proportions of participants who achieved the binary response at Week 12 as defined in the variable attribute above between the combined guselkumab group and the placebo group.

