5.5.1. Exploratory Clinical Endpoints

5.5.1.1. Mayo Score Based Endpoints

In addition to the primary endpoint analysis described in Section 5.3.1, clinical remission with definitions given in Table 10 will be analyzed at Week 12, Week 24 and Week 48.

Table 10: Clinical Remission Definitions for Week 12, Week 24 and Week 48

Identifier	Definition
Main definition (Week 24 and Week 48 only)	Stool frequency subscore of 0 or 1 and not increased
	from baseline, a rectal bleeding subscore of 0, and an
	endoscopy subscore of 0 or 1 with no friability present
	on the endoscopy (as given in Section 5.3.1)
Legacy definition	Defined as a full Mayo score ≤2 points, with no
	individual subscore >1 point
Alternative definition	Stool frequency subscore of 0, a rectal bleeding
	subscore of 0, and an endoscopy subscore of 0 or 1
	with no friability present on the endoscopy

In addition to clinical response analyses described in Section 5.4.1.1, analyses according to definitions in Table 11 will be performed for Week 12, Week 24 and Week 48.

Table 11: Clinical Response Definitions for Week 12, Week 24 and Week 48

Identifier	Definition
Main definition (Week 24 and Week 48 only)	Decrease from baseline in the modified Mayo score by
	\geq 30% and \geq 2 points, with either a \geq 1-point decrease
	from baseline in the rectal bleeding subscore or a rectal
	bleeding subscore of 0 or 1 (as given
	in Section 5.4.1.1)
Legacy definition	Decrease from baseline in the full Mayo score by
	\geq 30% and \geq 3 points, with either a \geq 1-point decrease
	from baseline in the rectal bleeding subscore or a rectal
	bleeding subscore of 0 or 1

Symptomatic remission as defined in Section 5.4.1.1 will be evaluated at all visits, overall and by ADT-IR stratification factor. In addition, the following clinical endpoints will be evaluated:

- Deep symptomatic remission (stool frequency subscore of 0 and rectal bleeding subscore of 0) over time
- Change from baseline in absolute stool number at each visit through Week 24.
- Mayo stool frequency subscore of 0 or 1 over time

- Mayo rectal bleeding subscore of 0 over time
- Time to symptomatic remission: Time from randomization to the date of first time meeting symptomatic remission definition through Week 24 / Week 48

In addition to evaluations done at individual timepoints, the following evaluations combining timepoints will be performed (all analyses based on primary/main definitions):

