• Time to being corticosteroid-free prior to Week 48 among participants who were receiving concomitant corticosteroids at baseline

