6.14. Appendix 14 Detailed Prohibited Changes in UC Medications Rules

[figure not shown]
Participants had a prohibited change in UC medication described below are considered to have experienced ICE 2 as defined in Table 6:

[figure not shown]
- Initiation of restricted medications (rectal 5-ASA compounds, parenteral or rectal corticosteroids, including budesonide and beclomethasone dipropionate)
- Initiation of the following prohibited concomitant therapies
 - Immunomodulatory agents other than 6-MP, AZA, or MTX (eg, 6-thioguanine, cyclosporine, mycophenolate mofetil, tacrolimus, sirolimus, ozanimod, tofacitinib, and other JAK inhibitors).
 - Immunomodulatory biologic agents (eg, TNFα antagonists, ustekinumab, vedolizumab, abatacept, anakinra).
 - Experimental IBD medications (eg, upadacitinib, etrolizumab, brazikumab, mirikizumab, risankizumab) or other investigational medications/therapies.
 - Thalidomide or related agents
- Initiation of oral corticosteroids (including budesonide and beclomethasone dipropionate) due to worsening of disease.
- Increase in the dose of oral corticosteroids (excluding budesonide and beclomethasone dipropionate) > 5 mg/day (prednisone equivalent) above the baseline dose due to worsening of disease:
 - Any number of days with increase from Week 0 through Week 12
 - 3 days or more with increase from Week 12 through Week 24
 - 7 days or more with increase from Week 24 through Week 48
- Increase in the dose of oral budesonide > 3 mg/day above the baseline dose due to worsening of disease:
 - Any number of days with increase from Week 0 through Week 12
 - 3 days or more with increase from Week 12 through Week 24
 - 7 days or more with increase from Week 24 through Week 48
- Increase in the dose of oral beclomethasone dipropionate > 5 mg/day above the baseline dose due to worsening of disease:
 - Any number of days with increase from Week 0 through Week 12
 - 3 days or more with increase from Week 12 through Week 24
 - 7 days or more with increase from Week 24 through Week 48
- Any switch among oral budesonide, oral beclomethasone dipropionate or other oral corticosteroids (excluding prednisone equivalent changes) due to worsening of disease.
- Initiation of oral 5-ASA compounds due to worsening of disease.
- Increase above baseline in the dosage of oral 5-ASA compounds due to worsening of disease.

- Change from one oral 5-ASA compound to another 5-ASA compound due to worsening of disease.

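### Time to symptomatic remission and time to corticosteroid-free are censored at intercurrent events that the SAP elsewhere counts as unfavourable, so the Kaplan-Meier curves show attainment at or above the failure-counted proportion

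*SAP*

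**What the plan says.** SAP 5.5.1.1 lists time to symptomatic remission, measured to the "date of first time meeting symptomatic remission definition through Week 24 / Week 48". SAP 5.5.1.3 lists "Time to being corticosteroid-free prior to Week 48 among participants who were receiving concomitant corticosteroids at baseline". Reaching either event is good for the participant.

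SAP 5.5.4 gives the time-to-event rule: "Participant data will be censored at last measurement prior to or at the time of any ICE in categories 1-4 and 6". Kaplan-Meier curves, estimates and p-values follow by intervention group. Participants without an event, or who left the study first, are "censored at the last measurement prior to or at that timepoint or their termination date". The paragraph names no estimand strategy.

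The other rules for the same ICEs are:

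- Primary estimand (SAP 5.3.2.1, text under Table 6): "This estimand acknowledges that having an ICE in categories 1-4 and 6 is an unfavorable outcome".
- Binary endpoints (SAP 5.5.4): "Participants with ICEs in categories 1-4 and 6 will be considered not to have achieved the binary endpoint".
- Continuous and ordinal endpoints (SAP 5.5.4): "Composite strategy (categories 1-4 and 6): Baseline values will be assigned from the point of ICE onward".

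ICE 5 (COVID-19 or regional-crisis discontinuation) is handled as observed for binary, continuous and ordinal endpoints and is not among the censoring events here.

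**The concern.** A participant with ICE 1-4 or 6 is a failure in the symptomatic remission rate at each later visit, but leaves the risk set of the symptomatic remission curve. Kaplan-Meier assumes that such a participant would have gone on to attain the event at the rate of those still followed. The ICE definitions make that unlikely for most categories:

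- ICE 4 (meeting rescue criteria, SAP 1.2) requires no endoscopic improvement at Week 12 and less than a 2-point partial Mayo improvement at Weeks 12 and 16.
- ICE 3 is discontinuation for lack of efficacy or UC worsening.
- ICE 1 is ostomy or colectomy.
- ICE 2 (SAP Appendix 14) includes, for worsening disease, "Increase in the dose of oral corticosteroids (excluding budesonide and beclomethasone dipropionate) > 5 mg/day (prednisone equivalent) above the baseline dose", which bears directly on becoming corticosteroid-free.

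ICE 6 also covers discontinuations unrelated to efficacy, where censoring may be closer to non-informative. The documents do not give the mix.

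At stake is how the curves are read. Attainment taken from them would be higher than a failure-counted analysis gives, and would rest on an assumption that the SAP does not state.

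**Working it through.** **The plan's own figure.** The SAP gives none for the time-to-event analyses. The nearest is the power for symptomatic remission at Week 24 in SAP section 3, Table 3: 30% against 60%, 133 per arm, more than 99%. Pooled SE = √(2 × 0.45 × 0.55/133) = 0.0610; unpooled SE = √((0.3 × 0.7 + 0.6 × 0.4)/133) = 0.0582; z = (0.30 − 1.96 × 0.0610)/0.0582 ≈ 3.10; power 99.9%. It reproduces and is not in dispute. The 30% and 60% serve below only as stand-ins, because they are visit rates and the curves show first attainment.

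**Direction.** Let p be the share of all participants who attain the event before any ICE, and q the share with an ICE first. If nothing else is censored before the end of the period,

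p ≤ 1-KM ≤ p/(1 − q).

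The lower limit applies when no ICE precedes the last event, and the upper when all ICEs precede the first. In 20,000 simulated data sets, 1-KM was never below p and equalled it in 1,520.

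**Size (assumed inputs).** At visit k, S is multiplied by (1 − r_k/n_k), and n_(k+1) = n_k − r_k − c_k. Here r_k is the share with a first event, c_k the share censored at an ICE, and n_k the share at risk. First events at Weeks 4, 8, 12, 16, 20, 24:

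- placebo 0.05, 0.05, 0.06, 0.05, 0.05, 0.04 (sum 0.30)
- guselkumab 0.08, 0.12, 0.14, 0.10, 0.09, 0.07 (sum 0.60)

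*One case in full:* placebo, q = 30%, all after the Week 16 visit. S at Week 16 is 0.79. The share at risk falls from 0.84 to 0.84 − 0.05 − 0.30 = 0.49, then 0.44. S at Week 24 = 0.79 × (1 − 0.05/0.49) × (1 − 0.04/0.44) = 0.645, so 1-KM = 35.5% against a failure-counted 30%.

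| Arm (p) | q | ICEs spread evenly, Weeks 4-20 | all ICEs at Week 16 | upper limit |
|---|---|---|---|---|
| Placebo (30%) | 10% | 31.8% | 31.3% | 33.3% |
| | 20% | 34.0% | 33.1% | 37.5% |
| | 30% | 36.8% | 35.5% | 42.9% |
| Guselkumab (60%) | 5% | 62.0% | 61.6% | 63.2% |
| | 10% | 64.3% | 63.5% | 66.7% |
| | 20% | 70.1% | 68.9% | 75.0% |

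**Treatment difference.** A failure-counted 30 points becomes (even spread / Week 16):

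- 27.5/28.0 with q = 30% placebo, 10% guselkumab
- 30.3/30.4 with 20%, 10%
- 32.5/32.2 with 10%, 10%
- 36.1/35.8 with 20%, 20%

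**Hypothetical reading.** Take placebo with q = 30%, and suppose that ICE participants would have had half the later event rate of the others. The hypothetical target is then 33.6%/32.8%, while 1-KM shows 36.8%/35.5%. The two agree only when the rates are equal.

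**Corticosteroid-free by Week 48.** With p = 40%, attainments at Weeks 12 to 48 in proportions 0.10, 0.22, 0.22, 0.14, 0.08, 0.06, 0.06, 0.05, 0.04, 0.03, and ICEs spread over Weeks 12-44 or all at Week 16, 1-KM is 41.8%/43.5% (q = 10%), 44.0%/48.1% (20%) and 46.7%/54.3% (30%). This path is rough: it places a tenth of attainments at Week 12, when the taper only begins.

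**Why precedence matters.** If half of the 30% placebo ICE participants leave the study at the ICE and stay censored at termination, the estimate is 32.8%/32.1%, not 30%.

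**The case against.** The strongest defence is that the censoring is a hypothetical strategy. Placebo participants who meet rescue criteria switch to guselkumab at Week 16, and censoring asks what would have happened without rescue. A composite strategy for visit rates and a hypothetical one for curves is a legitimate choice, and the rule is explicit and prespecified. Conversely, fixing ICE participants as non-events sets their later attainment to zero, although Protocol 4.2 allows that sham-rescued guselkumab participants may respond late.

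Part of this stands. The motive is sound, and a hypothetical analysis may be kept. But the SAP does not name the strategy, and naming it would not make equal later event rates plausible. Counting ICE participants as non-events also keeps post-rescue remissions from being credited to placebo, and it follows the SAP's own composite logic.

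Four stronger readings are tempting, and the documents do not support them:

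- *These ICEs imply a lower later rate by definition.* A participant entering with stool frequency 1, rectal bleeding 1 and endoscopy 3 can reach symptomatic remission on a 1-point fall and still meet the 2-point rescue criterion. A lower rate is likely, not definitional.
- *Starting oral corticosteroids censors people moving away from corticosteroid-free.* That endpoint is limited to baseline users, who would normally have stopped, and so had the event, before starting again. Dose increase is the relevant part of ICE 2. Even that can be brief: 3 days suffice between Weeks 12 and 24, and 7 days between Weeks 24 and 48.
- *Nothing planned bears on the assumption.* SAP 5.5.4.1 summarises symptomatic remission over time in the Rescue Analysis Set. It is descriptive, bears only on ICE 4, and does not say whether post-ICE data are used as observed. It is not a formal sensitivity analysis.
- *The by-visit binary rates already correct the curves.* They measure status at a visit; the curves measure first attainment.

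**Conclusion.** The point holds. The SAP censors two favourable-event endpoints at ICEs that it otherwise counts as unfavourable, and gives no reason. That 1-KM is at or above the failure-counted proportion is a property of the estimator and needs no assumption. The size does: under the assumed event paths and ICE shares, 30% reads about 31-37% and 60% about 62-70%. That the censoring is informative is a likely inference from the ICE definitions, weakest for ICE 6.

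A reader might infer that the rule favours guselkumab or threatens the trial's conclusions. Neither follows. The difference can shrink or grow with the ICE shares by arm, which the documents do not give. Only exploratory endpoints with nominal p-values are touched; the primary and secondary analyses and Type I error control are not. The change is worth making because it is cheap and removes an unstated assumption.

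**What to change.** In the time-to-event paragraph of SAP 5.5.4, for these two endpoints only:

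1. Keep participants with ICE 1-4 or 6 before the event as non-events, censored at the end of the analysis period (Week 24 or Week 48).
2. State that this prevails over the termination-date rule when a participant leaves the study after such an ICE.
3. As an alternative to 1 and 2, report cumulative incidence with the ICE as a competing event.
4. Keep ICE 5 as observed.
5. If wanted, retain the present censoring as a supplementary analysis, labelled as a hypothetical strategy and stating its equal-rate assumption.

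The cost is a few lines of SAP text and minor programming. Any cumulative attainment read from the curves becomes lower where ICEs occur, and it will still differ from the visit rates because the curves count first attainment.

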5.5.4.1. Subgroup Analyses

Subgroup analyses for subgroups defined by the stratification variables (ADT-IR yes/no, baseline endoscopic subscore moderate [2]/severe [3]) will be performed using the FAS for the following exploratory endpoints (all as defined in Section 5.5.1.2):

- Histologic improvement
- Histologic remission
- Combination of histologic remission and endoscopic improvement

The following analysis approach will be applied:

- The consistency of intervention effect will be evaluated, using the main estimand and handling missing data by the rules specified in Section 5.4.2.1.
- The adjusted treatment difference of the combined guselkumab SC group vs. the placebo SC group and the associated p-values and 95% confidence intervals will be provided. The treatment differences, p-values and confidence intervals will be obtained from a MH test stratified by the remaining stratification factor.

In addition, descriptive analyses will be performed for the rescue analysis set for the following endpoints:

- Clinical remission (primary definition as given in Table 10 only) at Week 48
- Symptomatic remission over time
- Change from baseline in partial Mayo score over time
- 8-week corticosteroid-free clinical remission at Week 48: Defined as being in clinical remission at Week 48 and not having received corticosteroids between Week 40 and Week 48
- Change from baseline in CRP concentration [mg/L] over time
- Change from baseline in fecal calprotectin concentration [mg/kg] over time

Descriptive analyses will be performed for the Week 12 Clinical Responder Analysis Set for the following endpoints:

- Clinical remission at Week 24 and at Week 48
- Symptomatic remission over time
- Deep symptomatic remission at Week 24 and at Week 48
- Mayo stool frequency subscore of 0 or 1 over time
- Mayo rectal bleeding subscore of 0 over time
- Clinical response at Week 24 and at Week 48
- Clinical response through Week 48 (at both Week 24 and Week 48)
- Endoscopic normalization at Week 24 and at Week 48
- Endoscopic improvement at Week 24 and at Week 48
- Change from baseline in CRP concentration [mg/L] over time
- Change from baseline in fecal calprotectin concentration [mg/kg] over time
- Deep symptomatic remission (Mayo stool frequency subscore of 0 and Mayo at rectal bleeding subscore of 0) over time

